4.1 Inclusion criteria

Patients eligible for inclusion in this study must fulfill all of the following criteria:

1. Written informed consent for the extension must be obtained before any assessment is performed.
2. Patients who have been enrolled and treated with double-blind study medication in the PARADIGM-HF study (protocol CLCZ696B2314) and are able to be safely enrolled into the open-label trial as judged by the investigator.

4.2 Exclusion criteria

1. Use of other investigational drugs at the time of enrollment, or within 30 days or 5 half-lives of enrollment, whichever is longer

2. History of hypersensitivity or allergy to any of the study drugs, drugs of similar chemical classes, ACEIs, ARBs, or NEP inhibitors as well as known or suspected contraindications to LCZ696
3. Known history of **angioedema**
4. Requirement of simultaneous treatment with both ACEIs and ARBs
5. Current acute decompensated HF (exacerbation of chronic HF manifested by signs and symptoms) that may require intravenous therapy
6. Symptomatic hypotension and/or a SBP < 100 mmHg at Visit 1 (screening)
7. Estimated GFR < 30 mL/min/1.73m² as measured by the simplified MDRD formula at Visit 1 (screening)
8. Presence of bilateral renal artery stenosis
9. Serum potassium > 5.2 mmol/L at Visit 1 (screening)
10. Evidence of hepatic disease as determined by any one of the following: AST or ALT values exceeding 3 x ULN at Visit 1, history of hepatic encephalopathy, history of esophageal varices, or history of porta-caval shunt
11. Pregnant or nursing (lactating) women, where pregnancy is defined as the state of a female after conception and until the termination of gestation, confirmed by a positive hCG laboratory test
12. Women of child-bearing potential, defined as all women physiologically capable of becoming pregnant, unless they are using **highly effective** methods of contraception during dosing and for **7 days after discontinuation of LCZ696 treatment**.

Highly effective contraception methods include:

- Total abstinence (when this is in line with the preferred and usual lifestyle of the subject).
 - Periodic abstinence (e.g., calendar, ovulation, symptothermal, post-ovulation methods) and withdrawal **are not acceptable methods** of contraception;
- Male sterilization (at least 6 months prior to Visit 1). For female subjects on the study, the vasectomized male partner should be the sole partner for that subject;
[For the United Kingdom ONLY: Male sterilization (at least 6 months prior to Visit 1): Prior to starting dosing of the female subject, medical assessment of the surgical success of the partner's vasectomy must be provided.]
- Combination of any two of the following (a+b or a+c, or b+c):
 - a. use of oral, injected or implanted hormonal methods of contraception (combined estrogen and progestogen or progestogen only) or other forms of hormonal contraception that have comparable efficacy (failure rate <1%), for example hormone vaginal ring or transdermal hormone contraception.
 - b. placement of an intrauterine device (IUD) or intrauterine system (IUS)
 - c. barrier methods of contraception: condom or occlusive cap (diaphragm or cervical/vault caps) with spermicidal foam/gel/film/cream/vaginal suppository
- In case of use of oral contraception women should have been stable on the same pill for a minimum of 3 months before taking study treatment.

- Women are considered post-menopausal and not of child bearing potential if they have had 12 months of natural (spontaneous) amenorrhea with an appropriate clinical profile (e.g. age appropriate, history of vasomotor symptoms) or six months of spontaneous amenorrhea with the appropriate hormonal profile, or have had surgical bilateral oophorectomy (with or without hysterectomy) at least six weeks prior to study treatment administration. In the case of oophorectomy alone, only when the reproductive status of the woman has been confirmed by follow up hormone level assessment she is considered not of child bearing potential.

13. Any condition, not identified in the protocol that in the opinion of the investigator is likely to prevent the patient from safely tolerating LCZ696 or complying with the requirements of the study.

If a patient has experienced a significant cardiovascular (e.g., acute coronary syndromes, stroke, transient ischemic attack) or non-cardiovascular event in the interim between the end of PARADIGM-HF and the start of CLCZ696B2317, the investigator should ensure that the individual is appropriately stable before enrolling them in the open-label study. If there is uncertainty about a patient's eligibility, the investigator should consult the study medical monitor to determine if the individual should be enrolled.

5 Treatment

5.1 Protocol requested treatment

5.1.1 Investigational treatment

All eligible patients will receive LCZ696 in addition to optimal CHF therapy, as considered appropriate by the investigator and in accordance with standard therapy guidelines, but with the exception of an ACEI or ARB as this will be replaced by LCZ696. The use of an ACEI or an ARB in addition to LCZ696 is strictly prohibited.

The Sponsor will provide the following open-label study medication in bottles:

- LCZ696 50 mg film-coated tablets (LCZ696 dose level 1)
- LCZ696 100 mg film-coated tablets (LCZ696 dose level 2)
- LCZ696 200 mg film-coated tablets (LCZ696 dose level 3)

Sufficient medication will be provided for treatment according to the study protocol, including additional medication to allow for delayed visits.

Medication labels will be in the local language and comply with the legal requirements of each country. They will include storage conditions for the drug.

The target p.o. dose of LCZ696 is 200 mg bid. For patients not tolerating the target dose, LCZ696 will be titrated down to a lower dose level twice a day, at the investigator's discretion, based on the defined safety and tolerability criteria ([Appendix 3](#), [Appendix 4](#) and [Appendix 5](#)).

For the initial treatment doses (50 or 100 mg bid) administered up to visit 2 and 3, the protocol indicates that the dose could be administered 1-to-2 weeks prior to the next visit. However, treatment should last for a **minimum of 1 week** before up-titrating to the next dose strength.

Recommended starting LCZ696 dose

For patients who tolerated **dose level 3** (either 200 mg LCZ696 bid or 10 mg enalapril bid) in the PARADIGM-HF study, the recommended starting dose is 100 mg LCZ696 bid. Similarly, for patients who maximally tolerated **dose level 2** (either 100 mg LCZ696 bid or 5 mg enalapril bid) in the PARADIGM-HF study, the recommended starting dose could be 100 mg LCZ696 bid. These patients can be up-titrated to 200 mg LCZ696 bid at a later time at the discretion of the investigator.

If, in the investigator's judgment, the patient may not tolerate the proposed starting dose of 100 mg LCZ696 bid, the patient could start with 50 mg LCZ696 bid and be up-titrated at the time of subsequent visits.

The starting dose of 50 mg bid is also recommended for patients who previously only tolerated dose level 1(either LCZ696 50 mg bid or enalapril 2.5 mg bid) in the PARADIGM-HF study.

Table 5-1 Recommended starting dose

Dose levels used in CLCZ696B2314	Study treatment in CLCZ696B2314	Corresponding starting dose in this study LCZ696, mg bid
1	50 mg LCZ696bid or 2.5 mg enalapril bid	50
2	100 mg LCZ696bid or 5 mg enalapril bid	50 or 100
3	200 mg LCZ696bid or 10 mg enalapril bid	50 or 100

If the patient is taking an ACEI at the time of enrollment, a **36-hour washout** period is required before starting treatment with LCZ696.

If LCZ696 is *permanently* discontinued, treatment with an appropriate dose of an ACEI and/or ARB should be initiated. A 36-hour washout period is also required before starting treatment with an ACEI after discontinuation of LCZ696.

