1.1 Background

Chronic heart failure (CHF) is a major public health problem characterized by significant mortality, frequent hospitalization, and poor quality of life, with an overall prevalence that is increasing throughout the world. In the United States (US) alone, approximately 5 million patients have heart failure (HF) and there are over half a million newly diagnosed cases annually (Hunt et al 2009, McMurray et al 2012). In Europe, the prevalence of HF is between 2 and 3%, and in the elderly is estimated between 10 to 20% (McMurray et al 2012). Medical therapies targeted at improving outcomes in HF with a low EF have been well studied over the past two decades, leading to an improvement in survival as well as a decrease in morbidity, mostly in the form of decreased re-hospitalization for HF. These medical therapies include angiotensin converting enzyme inhibitors (ACEIs), angiotensin receptor blockers (ARBs), β -blockers and mineralocorticoid antagonists (CONSENSUS Trial Study Group 1987, Cohn and Tognoni 2001, SOLVD Investigators 1991, SOLVD Investigators 1992, RALES Investigators 1996, Pitt et al 1999, MERIT-HF Study group 1999, CIBIS II Investigators 1999, Packer et al 2002, Pfeffer et al 2003, Flather et al 2005; Zannad et al 2011). However, despite advances in pharmacological (and device therapies), the outlook remains poor. Overall, 50% of patients die within 4 years and 40% of patients admitted to the hospital with HF die or are readmitted within 1 year (McMurray et al 2012). Thus, HF still represents a major cause of cardiac mortality and morbidity with a clear need for better therapy.

LCZ696 is a first-in-class, angiotensin receptor neprilysin inhibitor (ARNI) being developed for the treatment of heart failure. Following ingestion, LCZ696 provides systemic exposure to AHU377, a neprilysin (neutral endopeptidase 24.11, NEP) inhibitor (NEPi) and valsartan, an angiotensin receptor blocker (ARB). [REDACTED]

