3.3 Rationale of dose/regimen, route of administration and duration of treatment

Based on safety data from the PARADIGM-HF single-blind, sequential design run-in period, LCZ696 was well-tolerated, with over 90% of patients achieving the target dose.

A strong rationale exists for the target dose of LCZ696 in HF-rEF patients. A p.o. dose of LCZ696 200 mg bid delivers similar exposures of valsartan (assessed by AUC) as Diovan® 160 mg bid, the highest approved Diovan® dose for HF and the dose recommended in international guidelines for the treatment of HF. In addition, biomarker analysis (increase in ANP and cGMP) indicates that this dose delivers approximately 90% of its maximal NEP inhibition.

Most importantly, this study will target the oral dosing regimen for LCZ696 identical to that which showed a mortality and HF hospitalization benefit superior to that of enalapril in PARADIGM-HF.

[*] The study will continue in an individual country for a minimum of 12 months and until a marketing authorization has been received and the drug product becomes commercially available in that country (which is expected to be up to 30 months) from the date of the first eligible patient enrolled in that country, or until the study is terminated, whichever comes first. Within the study period, the duration of treatment for an individual patient will be at the discretion of the investigator.

[* For **Denmark only**, the above paragraph will read as follows:

From the date of the first eligible patient enrolled in Denmark, the study will have a duration of 12 months. The treatment duration may be re-evaluated and an amendment issued to adjust the treatment duration.]

[* For the **United Kingdom only** the above paragraph will read as follows:

From the date of the first eligible patient enrolled in the UK, the study has a minimum duration of 12 months and a maximum duration of 20 months. The treatment duration may be re-evaluated and an amendment issued to adjust the treatment duration].

[* For **Germany only**, the above paragraph will read as follows:

From the date of the first eligible patient enrolled in Germany, the study will have a maximum duration of 24 months. The treatment duration may be re-evaluated and an amendment issued to adjust the treatment duration.]

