5.5.5 Permitted dose adjustments and interruptions of study treatment

Every attempt should be made to maintain patients on the target LCZ696 dose level of 200 mg bid throughout the trial.

If in the opinion of the investigator, the patient does not tolerate the target dose of 200 mg LCZ696 bid (dose level 3), the investigator should consider the following:

1. whether non-disease-modifying medication (e.g., CCBs, diuretics, nitrates, α -blockers) can be reduced to rectify the situation, before reducing the dose of the study drug to a lower dose level (100 mg bid or 50 mg bid LCZ696).
2. may adjust doses of disease-modifying medications (e.g., β -blockers, aldosterone antagonists) if it is believed that they are the most likely cause of the adverse effect.

3. If adjustment/elimination of concomitant medications is not possible or does not alleviate the side effects of concern, the investigator may down-titrate the dose of the LCZ696 to:

- a. the next lower level

The patient should be re-challenged with a higher dose when the investigator feels it is appropriate to do so per the directions provided below in this section.

- b. complete withdrawal of the study drug

If the study drug is temporarily discontinued, it should be reintroduced as soon as medically justified in the opinion of the investigator.

If needed, LCZ696 may be discontinued in favor of starting the patient on an ACEI or ARB (minimum of 36 h between last dose LCZ696 and first dose of ACEI; 12 h between last dose LCZ696 and first dose of ARB).

Study drug dose level adjustments should mainly be based on overall safety and tolerability with special focus on:

- a) hyperkalemia ([Appendix 3](#): treatment guidelines for hyperkalemia);
- b) symptomatic hypotension ([Appendix 4](#): guidelines for management of BP);
- c) clinically significant decrease in eGFR/increase in serum creatinine ([Appendix 5](#): guidelines for management of renal dysfunction).

Any changes in the LCZ696 dose level must be recorded on the Dosage Administration Record eCRF and registered in the IRT.

Adjustment of study drug dose level

If despite adjustment of concomitant medications per the guidance provided above does not rectify the situation, the investigator may consider adjusting the dose of LCZ696 according to the following instructions.

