5.5.6 Rescue medication

Guidance on handling hyperkalemia, hypotension, and renal dysfunction are provided to investigators in [Appendix 3](#), [Appendix 4](#) and [Appendix 5](#), respectively. Patients may receive open-label ACEIs and/or ARBs during the study **ONLY** if LCZ696 has been discontinued. Resuming ACEI therapy requires a 36 h washout from the last LCZ696 dose.

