5.5.8 Prohibited treatment

5.5.8.1 ACEIs, ARBs and renin inhibitors

In this clinical trial, patients' pre-study ACEIs/ARBs will be replaced with LCZ696.

The concomitant use of open-label ACEIs or ARBs is strictly prohibited while the patient is receiving LCZ696. If the investigator believes that addition of an ACEI or ARB is necessary, then LCZ696 must be discontinued. In order to safely transition from LCZ696 to an ACEI, a period of 36 hours must transpire between the start of the last dose of LCZ696 and the start of the first dose of the ACEI (this is also true if transitioning from an ACEI to LCZ696). However, if the investigator discontinues LCZ696 and replaces it with an ARB, only 12 hours

must transpire between the start of the last dose of LCZ696 and the start of the first dose of the ARB (i.e., the next regularly scheduled dose).

Concomitant administration of renin inhibitors, such as aliskiren, is also prohibited.

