7.6 Pregnancy reporting

In case a patient becomes pregnant, or plans to become pregnant, LCZ696 must be discontinued permanently. To ensure patient safety, each pregnancy occurring while the patient is on LCZ696 treatment must be reported to the Sponsor within 24 hours of learning of its occurrence. The pregnancy should be followed up to determine outcome, including spontaneous or voluntary termination, details of the birth, and the presence or absence of any birth defects, congenital abnormalities, or maternal and/or newborn complications.

Pregnancy should be recorded on a Clinical Trial Pregnancy Form and reported by the investigator to the Sponsor's local Drug Safety and Epidemiology Department. Pregnancy follow-up should be recorded on the same form and should include an assessment of the possible relationship to LCZ696 treatment.

Any SAE experienced during pregnancy must be reported on the SAE Report Form.

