10.2 Informed consent procedures

Eligible patients may only be included in the study after providing written (witnessed, where required by law or regulation), IRB/IEC-approved informed consent, or, if incapable of doing so, after such consent has been provided by a legally acceptable representative(s) of the patient. In cases where the patient's representative gives consent, the patient should be informed about the study to the extent possible given his/her understanding. If the patient is capable of doing so, he/she should indicate assent by personally signing and dating the written informed consent document or a separate assent form. Informed consent must be obtained before conducting any study-specific procedures (i.e. all of the procedures described in the protocol). The process of obtaining informed consent should be documented in the patient source documents.

The Sponsor will provide to investigators in a separate document a proposed informed consent form that complies with the ICH GCP guideline and regulatory requirements and is considered appropriate for this study. Any changes to the proposed consent form suggested by the investigator must be agreed to by the Sponsor before submission to the IRB/IEC, and a copy of the approved version must be provided to the Sponsor's monitor after IRB/IEC approval.

Women of child bearing potential should be informed that taking the study treatment may involve unknown risks to the fetus if pregnancy were to occur during the study and agree that in order to participate in the study they must adhere to the contraception requirement for the duration of the study. If there is any question that the patient will not reliably comply, they should not be entered in the study.

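### The advice to start an ACEI or ARB after any permanent stop of LCZ696 makes no exception for pregnancy; a smaller gap leaves the stop and restart rules for clinically significant angioedema unclear

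*Protocol*

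**What the plan says.** **Pregnancy.** Protocol section 5.1.1, after Table 5-1, covers what follows when LCZ696 is permanently "discontinued, treatment with an appropriate dose of an ACEI and/or ARB should be initiated". Its only qualifiers are the appropriateness of the dose and a 36-hour washout before an ACEI. Section 7.6 states: "In case a patient becomes pregnant, or plans to become pregnant, LCZ696 must be discontinued permanently". Section 5.5.9 also has pregnancy on its required-stop list. Section 1.1 describes LCZ696 as giving exposure to a neprilysin inhibitor "and valsartan, an angiotensin receptor blocker (ARB"). Section 10.2 has women of child-bearing potential told that "taking the study treatment may involve unknown risks to the fetus if pregnancy were to occur during the study".

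**Angioedema.** Section 5.5.9 has two lists. The required stops are withdrawal of consent, pregnancy, and the investigator's view that continuing would harm the patient. The discretionary stops are a severe suspected drug-related adverse event and suspected angioedema. The angioedema bullet adds that clinically significant signs or symptoms call for thorough evaluation and are a reason to discontinue. Section 5.5.5 says that LCZ696 should be brought back after a temporary stop once the investigator finds it medically justified, and does not mention angioedema. Section 4.2, exclusion 3, bars anyone with a known history of angioedema from entry. Appendix 3 forbids resumption after potassium of 6.0 mmol/L or more without case discussion with, and permission from, the sponsor's medical monitor.

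**The concern.** Two instructions meet in the same patient. One requires the drug to stop for good because of pregnancy. The other then advises starting an ACEI or an ARB, and an ARB is one of the two components of the drug just stopped. The advice takes effect as the patient leaves the study: under section 5.5.9 a permanent stop is withdrawal, with a final visit and no later assessments unless an adverse event needs follow-up. A site following the text literally would therefore act on it when study oversight is ending.

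For angioedema the problem is ambiguity. One bullet is headed as discretionary but worded as though clinically significant cases should lead to a stop, so sites could handle the same event differently. If a site treats the stop as temporary, the general restart rule applies, and the patient could return to LCZ696 with a history that would have kept them out at screening.

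Patient safety is at stake in both cases. The trial's estimates are not.

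**Working it through.** No arithmetic applies, so the check is a reading of the relevant sections side by side.

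**Pregnancy**

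1. *Is the stop permanent?* Yes. Section 7.6 says so for actual and planned pregnancy, and section 5.5.9 makes pregnancy a required stop.
2. *Does a permanent stop trigger the ACEI/ARB advice?* Yes. That is the condition stated in section 5.1.1. The phrase on dose governs how much to give. It does not govern whether to start.
3. *Does the advised class overlap with the stopped drug?* Yes for an ARB (section 1.1).
4. *Does the protocol treat LCZ696 as unsuitable in pregnancy?* Yes. Exclusion 11 bars pregnant and nursing women, exclusion 12 requires highly effective contraception, and section 10.2 has women warned of possible fetal risk.
5. *Is there an exception elsewhere?* None was found. Section 7.6 covers reporting and follow-up and says nothing about replacement therapy. Sections 5.5.5, 5.5.6, 5.5.8.1 and 5.5.9 do not link an ACEI or ARB to the reason for stopping. Section 9.3 repeats the expectation that patients go back to an ACEI or ARB, though only to say how those drugs are reported.

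Steps 1 to 3 produce the conflict, and step 5 shows that nothing resolves it.

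**Angioedema**

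1. *Is it named on the required-stop list in section 5.5.9?* No. It is named only on the discretionary list.
2. *Can the required list still reach it?* Yes, through the item on harm to the patient's well-being, if the investigator takes that view.
3. *Does section 5.5.5 bar restart after it?* No. Restart depends on medical justification alone.
4. *Do sections 7.7 and 8.5 fill the gap?* No. They cover the questionnaire, reporting to the sponsor and adjudication, but give no rule on treatment.
5. *Does the protocol write such a rule for another serious risk?* Yes. At potassium of 6.0 mmol/L or more, Appendix 3 requires an immediate stop and sponsor permission before resumption.

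Angioedema excludes at entry and receives dedicated reporting. It has neither an unambiguous stop nor a restart condition during treatment.

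**The case against.** The best defence is that these texts leave room for clinical judgment. Section 5.1.1 advises and does not command. Section 5.5.9 already points toward stopping for clinically significant angioedema, and its required list has an item broad enough to cover it. Restart under section 5.5.5 needs medical justification and arises only if the stop was treated as temporary. The Investigator's Brochure, which was not available here, may say more. All of this stands and lowers the risk. It does not remove the pregnancy conflict, because there the written advice itself points the wrong way.

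Several stronger readings are tempting, and the documents do not support them:

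- *The switch would leave ARB exposure unchanged.* A reader might infer this from the statement in section 3.3 that "LCZ696 200 mg bid delivers similar exposures of valsartan (assessed by AUC") as a full valsartan dose. It would need the site to choose valsartan at that dose. Section 5.1.1 names no drug or dose, and another ARB or an ACEI would supply no valsartan. The 12 hours in section 5.5.8.1 ("if the investigator discontinues LCZ696 and replaces it with an ARB, only 12 hours") is a minimum gap and does not tell anyone when to start.
- *The whole protocol pushes an ACEI or ARB after a stop.* Sections 5.5.5 ("If needed, LCZ696 may be discontinued in favor of starting the patient on an ACEI or ARB") and 5.5.6 ("Patients may receive open-label ACEIs and/or ARBs during the study") permit these drugs, and 5.5.8.1 sets washout rules for elective switches. None directs treatment after a stop for pregnancy.
- *An ACEI or ARB after angioedema is a further defect.* The documents state no such harm. Exclusion 3 concerns entry to LCZ696 treatment.
- *Section 6.5.6 shows that restart rules exist for comparable events.* Its negative-test condition resolves a possibly false-positive urine test. It is not a rule for restarting after pregnancy.

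**Conclusion.** The pregnancy point holds as an internal inconsistency in section 5.1.1, read with sections 7.6 and 1.1. The angioedema point also holds but is secondary: the stop rule is ambiguous and the restart rule is silent, with investigator judgment narrowing the gap.

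The size cannot be put in numbers, because the documents give no rate of pregnancy or angioedema. That both will be uncommon is an assumption. It is reasonable given required contraception for women of child-bearing potential and exclusion of known angioedema at entry. The analysis is unaffected: this is a single-arm descriptive safety study with no treatment comparison, and no analysis set, table or method depends on these sentences.

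A reader might infer that the protocol calls ACEIs and ARBs contraindicated in pregnancy. It does not say so. The conclusion rests only on the protocol's decision to stop a drug containing an ARB for pregnancy, followed by unconditional advice to start an ACEI or ARB. Nor does it follow that any patient would be mistreated; the finding is that literal compliance permits it.

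**What to change.** 1. **Section 5.1.1:** qualify the ACEI/ARB advice so that it applies unless contraindicated by the reason for the stop, giving pregnancy and planned pregnancy as the examples.
2. **Section 5.5.9:** move clinically significant angioedema, as judged by the investigator, to the required-stop list. Keep discretion for cases that are only suspected.
3. **Section 5.5.5:** state that LCZ696 is not restarted after clinically significant angioedema.

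The investigator's judgment should define the category. Tying it to the adjudication committee would need a new process, because the protocol sets no timeline for adjudication and no return of its result to sites.

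The cost is a protocol amendment under section 11.1, with the approvals it requires, and a site letter. No visits, tests or patients are added and the analysis plan does not change. The one clinical downside is that patients with clinically significant angioedema lose the option of rechallenge.
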